2.2 Study Rationale

Interdisciplinary pain management is now a high priority for the DoD and VHA. The United States Army assembled a Pain Management Task Force in 2009 with the mission of outlining gaps in chronic pain management resources throughout the DoD and VHA medical systems. It completed site visits with pain management specialists at VHA and DoD facilities throughout the United States (including with the PI of this proposed research) to identify potential best practices in military chronic pain management. In its 2010 Final Report, the Task Force emphasized a need for pain management resources that go beyond medication and other one-dimensional interventions, specifically emphasizing the need for Complementary and Alternative Medicine (CAM) approaches. They noted that most DoD and VHA providers feel ill-prepared to manage chronic pain and are unaware of resources for pain management beyond medications and physical therapy. Specifically, the report outlined the need for standardized interdisciplinary programs offering improved pain management with the benefit of decreased risk of opioid abuse. These interdisciplinary programs are likely to result in vast improvements in function, healthcare utilization, and quality of life for military Veterans with chronic polymorbid pain ([name] et al., 2006; [name] et al., 2010), and would severely decrease adverse risk associated with long-term opioid use/abuse in this population saving the federal government billions of dollars in healthcare costs. The study PI recently published a paper in the *American Psychologist* (March 2014) describing the significant benefit of integrated/interdisciplinary pain management programs over independent pain management interventions (Gatchel, [name], [name] & Lippe, 2014). In this paper, the authors note that psychological interventions for chronic pain are most useful as an embedded component of a larger, multi-component program including

disciplines oriented toward improving physical functioning. This is particularly important for military and Veteran populations for whom physical functioning is a vital part of their jobs and identities. When developed well and integrated appropriately, psychological interventions can significantly enhance and improve outcomes from other pain management interventions (e.g., PT). Previous studies of interdisciplinary pain programs (including the original FORT study) have consistently shown that these interdisciplinary programs outperform individual treatment like PT.

Some steps have already been taken to develop interdisciplinary care for polymorbid Veterans. In 2004, the U.S. Congress passed Public Law 108-422, Section 302 and Public Law 108-447, both of which require the development of integrated VHA specifically addressing deployment-related polymorbidity (Cifu et al., 2009; Eapen et al., 2013). One consequence of this legislation was the establishment of the VHA Polytrauma System of Care (PSC), which built and staffed 5 Polytrauma Rehabilitation Centers (PRCs) across the United States to serve as referral hubs for OEF/OIF/OND Veterans with complex polymorbid conditions. These PRCs currently offer the highest level of intervention available to polymorbid Veterans. Despite these advances, there are still significant gaps in the management of complex chronic polymorbid pain that severely challenge caregivers and Veterans alike. PRCs are equipped with multiple disciplines necessary to adequately address the complexity of polymorbid chronic pain, but these services are not adequately integrated for polymorbid pain management [9]. This integration is difficult, and there are very few interdisciplinary pain management programs that have been proven effective in military-relevant pain populations. Our research team was one of the first to test a truly integrated model of pain management in a military population which we called the Functional Orthopedic Treatment program (FORT). Recently, the Affordable Care Act has laid out plans and instructions for the proliferation and promulgation of interdisciplinary pain management services (see Gatchel, [name], [name] & Lippe, 2014).

The FORT program was originally tested in a non-polymorbid active duty military chronic pain sample. The original trial showed that our model of integrated care can effectively improve physical and psychosocial disability among military service members with pain. It has yet to be tested in a polymorbid pain population, but we believe that the CAM-based composition of FORT makes it an excellent substrate for polymorbid pain management. We have expanded on the original FORT trial through several subsequent trials specifically focusing on pain processes in polymorbid military members and Veterans. Data from these subsequent trials have allowed us to tailor the FORT intervention to the specific needs of a polymorbid OEF/OIF/OND Veteran chronic pain population. We have labeled this amended version of the manualized program “FORT-A” (A = Amended), and believe that this new program offers the best available opportunity for polymorbid pain management. The proposed study will recruit 130 OEF/OIF/OND Veterans with polymorbid chronic musculoskeletal pain who are currently using chronic opioid therapy for pain (taking opioid medications daily for 20 out of 30 days a month for three or more months). In 2015, the VA Opioid Safety Initiative (OSI) began to programmatically work toward improving the safety of opioid medication prescription for San Antonio Veterans with chronic pain. As noted above, very little is known about the potential outcomes of this initiative, but the scant available data suggest a rate of opioid recidivism of 30-40% among prior persistent opioid users who get no specialty intervention. To align with this initiative, this study altered the opioid inclusion criterion to include Veterans who were removed from opioid medications during the OSI. These Veterans will be randomly assigned to either the 3-week interdisciplinary FORT-A chronic pain management program (described below) or to

treatment in the South Texas Veterans Health Care System’s (STVHCS) PRC in San Antonio, TX, which represents the best available care for Veterans with deployment-related polymorbid pain. Primary endpoints for this research include pain management (represented in Aim 1) and opioid use (represented in Aim 2) at pre-treatment, post-treatment, 6-month follow-up and 12-month follow-up.

3. STUDY DESIGN

To address the primary and secondary hypotheses, this research study was designed as a randomized clinical trial comparing the manualized FORT-A treatment to treatment as usual for polytraumatic chronic musculoskeletal pain in the STVHCS Polytrauma Rehabilitation Center. Eligible OEF/OIF/OND Veterans will be randomized to either arm in 1:1 random permuted block randomization with no stratification. Because the FORT-A is a group intervention, it is vital that we randomize into meaningful blocks of at least three Veterans and no more than seven. Three is chosen as the lower block boundary because the PI had success in the original FORT trial with FORT groups of three active duty service members. Seven Veterans will be the upper boundary because FORT groups of more than seven military members were difficult to manage. In block randomization with static boundaries, study staff overseeing randomization will lose blinding if they are aware of how many participants have already been randomized into each block. For example, if block boundaries are always 5 participants and the treatment as usual condition has 5 participants while the active treatment has 4, then the staff randomizing the 10th participant will know with certainty that this participant will be in the active treatment group. To protect blinding, we have chosen to implement a variable boundary randomization for which the study staff randomizing patients will be blind to the boundaries and the resulting condition of the participant (see Sanghaei, 2011). The PI, Independent Evaluators, and Biostatistician will be blind to the condition of all participants until data lock. A research assistant overseeing randomization will also be blinded by randomizing unique patient identifiers into variable permuted blocks (through the STRONG STAR Data Core) by unique study identifier (e.g., first participant identified as #0001). All assessments given by Independent Evaluators will be labeled with just the unique identifier. Only the study coordinator (and co-coordinator) will be able to link unique identifiers to individual participants.

This research study covers two objectives/aims encompassing four formal hypotheses and one exploratory objective. The primary objective of this research is to assess the efficacy of the FORT-A program for improved pain management in a sample of 130 polymorbid OEF/OIF/OND PRC-eligible Veterans with chronic musculoskeletal pain compared to standard care in the STVHCS Polytrauma Rehabilitation Center. A second objective will assess the efficacy of FORT-A in decreasing the rate of opioid use among eligible Veterans with recent and ongoing persistent opioid use. An exploratory objective will explore how certain variables (helplessness and perceived burdensomeness) contribute to change trajectory over time.

Table 1. Pearson correlation between 4 disability measures and other notable FORT outcomes.

Pearson's r	FTW	WTE	ODI	MVAS
Depression	-.174	-.278	.690	.424
Fear Avoidance	-.106	-.184	.622	.530
Pain Rating	-.099	-.219	.856	.816

The primary outcome of this research (addressing AIM 1) is disability rating (consistent with functional restoration theory emphasizing functional ability over changes in pain intensity, frequency, duration, or

quality). This study was designed to assess disability objectively (functional capacity evaluation; FCE) and subjectively (self-reported disability scale). Data from the original FORT trial revealed that self-reported disability had a stronger relationship with psychosocial and socioeconomic pain management outcomes than objective functional capacity (see Table 1 for an example). Furthermore, self-reported disability is likely to be more sensitive to improvements in psychological pain management skills (which is central to this research). For this research study, the Oswestry Disability Index (ODI, Version 2) will be used to measure self-reported disability. ODI was chosen for this purpose because the significant body of research supporting its use and its performance beyond other measures of self-reported disability in the FORT trial.

The secondary outcome (addressing AIM2) for this research is rate of opioid medication recidivism. In consultation with study co-I and opioid dependence/misuse expert, [name], we decided to adopt a conservative definition of recidivism of use of any opioid for three days in any 30-day period. This definition was chosen (instead of a non-abstinent definition as described in McCabe et al., 2013) because this medical population may include veterans given short-term opioid therapy for a new injury or surgery and we did not want to count that as relapse or recidivism to opioid use. As was the case for disability, opioid use will be assessed through objective (MEMS caps) and subjective (timeline followback interview; TLFB) methods. Because some participants may shift patterns of other pain medication use as a result of discontinuing opioids, we will also complete TLFB for other pain medications and ask participants to use MEMS for their “most helpful” pain medication (if they are not taking an opioid med). All opioid medication use will be measured with MEMS and TLFB. We will also assess pain medication using the Medication Quantification Scale – III (MQS). The MQS was developed through the American Pain Society as a standardized method of quantifying pain medication use along dimensions of drug class, drug dose, and drug detriment (Harden et al., 2005). Both TLFB and MQS data will be gathered monthly (at all assessment intervals in person) and during monthly reminder phone calls. Previous studies have shown that Timeline Followback interviews demonstrate the best reliability and validity for long-term medication use (Kunoe et al., 2009), so TLFB was chosen as the focal secondary outcome measure for this research.

[figure not shown]
Based on our previous FORT trial, for which treatment effects in the FORT study arm were maintained at one-year follow-up, it is reasonable to assume that treatment benefits will be maintained after post-treatment and that all post-baseline measures can be averaged for a main effect of treatment. To detect a medium effect with power = 0.80 (based on Cohen’s standardized mean difference $d=0.50$) at $\alpha = 0.05$, we would require $n=50$ in each study arm for a total sample size of $N=100$ for data analysis. Based on our prior FORT research trial and our ongoing VA trials through STRONG STAR, we anticipate less than 30% attrition with a target recruitment goal of $n=65$ in each arm to account for dropouts. Thus the recruitment target for this research is 130 OEF/OIF/OND Veterans with military service-related new onset or exacerbated chronic musculoskeletal pain and persistent opioid use. Both the FORT-A and PRC treatments will be provided on an outpatient basis through the STVHCS PRC (where the PI has several hundred square feet of research space under a VA WOC appointment; see 5.1 and 5.2 in

this document for a more detailed description of the treatment arms). The overall trial will last 5 years (2014-2019). The IRB protocol for this research was approved on July 10, 2014 (see study binder for most current IRB documents and any amendments submitted and approved to the UTHSCSA/VA IRB). Individual participants will be actively enrolled for one year during which time they will:

- Complete pre-treatment assessments
- Undergo a three-week treatment phase
- Complete post-treatment assessment
- Complete 6-month post-treatment follow-up assessments
- Complete 12-month post-treatment follow-up assessments

The following diagram (Figure 2) outlines the administration for this research and the blinding status of individual study personnel/roles:

Figure 2. Study organizational hierarchy

Key:

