AIM 2: Assess the efficacy of FORT-A for decreasing the rate of opioid recidivism (using any opioid for 3 or more days in any 30-day period) compared to standard PRC care in a sample of OEF/OIF/OND polymorbid CMP Veterans discharged off of opioid medication in VA care since the start of the OSI. Unlike the original FORT trial, this research will formally and prospectively track opioid medication use among polymorbid Veterans to sensitively detect changes in chronic opioid therapy attributable to FORT-A versus PRC treatment. FORT-A is expected to produce significant reductions in the rate of opioid recidivism by imparting numerous strategies to supplant opioid medication as a pain management strategy. FORT-A will avoid the stigma of “traditional” opioid abuse treatment and provide a pain management alternative to those who have been discharged from opioid medications as part of the OSI.

EXPLORATORY AIM 3: Based on the PI’s ongoing ESCAPE trial, this research team has identified psychological processes (helplessness, perceived burdensomeness) that likely play a mechanistic role in pain management among OEF/OIF/OND deployers. We will assess these constructs twice a week and analyze latent changes in FORT-A and PRC Veterans to ascertain their role as pain management mediators

Design and Outcomes

This study is a 1:1 block randomized clinical trial comparing the FORT-A program to treatment as usual for polytrauma OEF/OIF/OND Veterans with prior persistent opioid use and chronic musculoskeletal pain who are eligible for treatment through the STVHCS Polytrauma Rehabilitation Center. All participants will be offered Physical Therapy services before enrollment and will be enrolled after completing or denying Physical Therapy (up to 12 sessions as recommended by a PRC Physical Medicine & Rehabilitation Physician ([name], [name]). If they have already completed PRC Physical Therapy before study enrollment, they will not need to do so again. Also, if the Veteran qualifies but refuses PRC Physical Therapy, he or she will still be eligible to enroll in this study and will not be asked to complete PRC PT. Veterans randomized to PRC (treatment as usual) will then meet with PRC and other VA medical providers per usual standards of care (described below). Those

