9.2 Sample Size and Randomization

The study is powered to detect a clinically meaningful difference between the two intervention groups on the primary outcome (ODI score) at the 12-month follow-up time period. This endpoint was chosen as it represents the durability of the treatment effect and best reflects the potential utility of the FORT-A program for improving the life of patients. The effect sizes used in the calculation are based on our previous FORT trial, for which treatment effects in the FORT study arm were maintained at the one-year follow-up.

Although Aim 2 changed in September 2015, it is important to note that the study must be powered for Aim 1 for two reasons. First, Aim 1 represents the most immediately relevant clinical endpoint, demonstrating that the FORT-A program is clinically superior to Treatment As Usual in this complex patient population. Second, the PI's previous military FORT study revealed a significant decrease in opioid medication use for program completers (compared to TAU). The resulting data suggest that improved pain management through functional restoration is a likely mechanism opioid medication reduction in military pain populations. Thus, Aim 1 must be met to maximize between-groups differences in Aim 2.

To best assess Aim 2, we have chosen to assess medication (opioid and non-opioid) use on a monthly basis (during follow-up assessments and monthly phone calls) using the TLFB and the MQS. The increased frequency in assessment (each measure will be given 12 times) will provide ample power to detect between-groups difference in opioid recidivism over the 12-month study period. Assuming a sample size of $N = 130$ ($n = 65/\text{group}$), 12 data collection periods (monthly follow-ups for one year), and a statistical significance level of 0.05, the analysis will have power = .80 to detect a clinically meaningful difference between the study groups. For example, if the control group exhibits a recidivism rate of 45% (as suggested in Section 2.1 of this document) and the active treatment group exhibits a recidivism rate of 22.5%, the study will have power = .80.

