Medication Data will be adjudicated by the PI, the Research Coordinator, and [name] (an expert in trauma and addiction comorbidity). Timeline followback interview and MQS-III data will be discussed for each participant by the IE and the Coordinator within two business days of each assessment. If there are any noted problems with the TLFB data, then the assessment will be adjudicated by the above sub-committee within 2 days of review. MEMS cap data will be gathered for each participant's reported "most helpful" pain medication and any opioid medications they are prescribed by VA or other providers outside the VA system during the course of the study. MEMS data will be downloaded for each participant at each assessment follow-up visit. Upon download, the IE will scrutinize downloaded data to ensure that it falls within an expected range. If aberrant or missing data are noted, these will be adjudicated with the above sub-committee (and potentially discussed with the manufacturer if hardware or software problems are suspected) in a deidentified format.

The primary opioid endpoint will be the timeline followback (TLFB) interview. The TLFB represents the primary measure of opioid use because of its reliability and sensitivity as a daily measure of opioid use and its lack of perceived stigma compared to regular urine tox screen. A trained and masked IE will administer TLFB asking participants about any opioid medication use and use of other medications for pain. The TLFB Interview for this study was adapted from Sobell and Sobell (1992) as a semi-structured clinical interview asking the participant to use a blank calendar to describe the number of pain pills taken each day for 30 days. Instructions are provided to help the interviewer guide the participant in completing the recall as accurately as possible. This method has been reliably used in other trials of medication/opioid use and abuse (Kunoe et al., 2009).

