AIM 2: Assess the efficacy of FORT-A for decreasing the rate of opioid medication recidivism compared to standard PRC care in a sample of OEF/OIF/OND polymorbid LBP Veterans. To examine our primary hypothesis, we will compare the rate of opioid medication recidivism between the two groups monthly from baseline to 12-month follow-up. As noted above, 30-40% of TAU participants are expected to meet criteria for opioid recidivism (use of any opioid medication for 3 days or more in the last 30 days at each assessment). A statistically significant main effect will be interpreted as the groups exhibiting differential change in regards disability. Secondary analyses will be conducted using growth curve modeling (i.e., mixed effects hierarchical regression with polynomial change parameters to model differences in the trajectory of opioid use over time between the groups by time).

EXPLORATORY AIM 3: To examine the role of helplessness and perceived burdensomeness in predicting the trajectory of change over time, we will use latent

growth curve modeling. We will first model the trajectory of change in the two primary outcomes as a function of group (Aim 1 and Aim 2). We will then model the trajectories of helplessness and perceived burdensomeness as a function of group. Assuming both associations are observed (i.e., that group status is related to changes in the outcomes and the mediators), we will conduct hierarchical entry of group status and each mediator to examine if group status is still associated with outcome after adjusting for changes in the mediators. This will allow us to assess the role of the mediators in predicting the outcome and the proportion of change trajectory attributed to changes in these mediators.

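### The 3-days-in-30 recidivism rule counts acute opioid courses of 3 or more days, which Section 3 says should not count, so Aim 2 mixes acute treatment with relapse

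*Combined protocol and SAP*

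**What the plan says.** Section 3 adopts "a conservative definition of recidivism of use of any opioid for three days in any 30-day period". It prefers this to a non-abstinence definition because participants may be given "short-term opioid therapy for a new injury or surgery and we did not want to count that as relapse or recidivism to opioid use".

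The rule appears in two other places. Aim 2 in the Précis has "using any opioid for 3 or more days in any 30-day period". Section 9.6 has "use of any opioid medication for 3 days or more in the last 30 days at each assessment", with the arms compared monthly up to the 12-month follow-up. None of the three statements refers to the reason for use.

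Section 9.5.2 makes the TLFB the primary opioid measure. The evaluator administers it by "asking participants about any opioid medication use and use of other medications for pain", and the participant uses a calendar "to describe the number of pain pills taken each day for 30 days". No item on the reason for use is described. On adjudication the section says: "If there are any noted problems with the TLFB data, then the assessment will be adjudicated". CPRS and the state prescription database (PAT) are consulted at the one-year visit to identify prescriptions; reclassifying episodes is not mentioned.

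Section 9.2 states power of 0.80 for Aim 2 with 65 per arm, assuming 45% recidivism in the control arm and that "the active treatment group exhibits a recidivism rate of 22.5"%.

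**The concern.** The stated purpose of the definition turns on why the opioid was taken. The rule looks only at how many days it was taken. A participant given an opioid on 3 or more days in 30 after an operation or a new injury is counted as a recidivist, and nothing in the interview, the adjudication or the record review as described would separate that course from relapse.

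The protocol itself makes such events plausible. Section 5.4 mentions shoulder surgery in a participant of the original FORT trial. Section 5.1 lists musculoskeletal injury as a risk of physical therapy. Section 7.3 uses a new injury as its example of an unrelated serious event. The Précis says usual care may include injections and other medical interventions. The arms differ in exercise and procedures, so equal rates of acute courses cannot be taken for granted.

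Two things are at stake. If the rates are equal, both recidivism proportions rise and their difference shrinks. If they are unequal, part of the observed difference has nothing to do with relapse.

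**Working it through.** **Inputs from the documents.** 65 per arm, 45% control, 22.5% FORT-A, alpha 0.05, 12 monthly assessments and stated power 0.80 (Section 9.2). The test is taken as two-sided, which Section 9.2 states for Aim 1 only.

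**Assumed input.** q is the share of participants, otherwise not recidivists, who meet the rule only through an acute course of 3 or more days. The documents give no value. The range used is 5% to 15%, with 45% and 22.5% taken as rates without acute courses.

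**Step 1: the plan's figure.** Pooled-variance normal approximation, with p̄ the mean of the two proportions:

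power = Φ{(|p₁ − p₂| − 1.96·√[2p̄(1 − p̄)/n]) / √[(p₁(1 − p₁) + p₂(1 − p₂))/n]}

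For 0.45, 0.225 and n = 65: (0.225 − 1.96 × 0.0829)/0.0806 = 0.775, so power = 0.78. With unpooled variance it is 0.80. The stated figure is reproduced by a simple two-proportion test on all 65 per arm.

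**Step 2: equal acute rates, one result per participant for the year.** Each proportion becomes p′ = p + (1 − p)q, so the difference becomes (1 − q) × 22.5 points.

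| q in each arm | Control | FORT-A | Difference (points) | Power |
|---|---|---|---|---|
| 0 | 45.0% | 22.5% | 22.5 | 0.78 |
| 5% | 47.8% | 26.4% | 21.4 | 0.72 |
| 10% | 50.5% | 30.3% | 20.3 | 0.66 |
| 15% | 53.3% | 34.1% | 19.1 | 0.60 |

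**Step 3: unequal acute rates, same endpoint.**

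| q control | q FORT-A | Control | FORT-A | Difference (points) | Power |
|---|---|---|---|---|---|
| 5% | 10% | 47.8% | 30.3% | 17.5 | 0.53 |
| 10% | 5% | 50.5% | 26.4% | 24.1 | 0.81 |

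In the second row the difference exceeds 22.5 points with no change in relapse.

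**Step 4: the monthly reading of Section 9.6.** A short course now affects only the 30-day window or windows it falls in, taken here as one or two of 12. The effective share per window is q/12 to 2q/12. With the same formula:

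| q over the year | Effective q per window | Power |
|---|---|---|
| 10% | 0.8% to 1.7% | 0.77 to 0.76 |
| 15% | 1.25% to 2.5% | 0.77 to 0.75 |

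This step isolates the dilution. It does not model the correlation between monthly assessments.

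**The case against.** The strongest reply is that the rule does serve its purpose in part. Section 3 justifies it against a stricter alternative. If that alternative would count any use at all, the 3-day threshold is a real move in the intended direction, because use on 1 or 2 days is left out. This stands. A reader might infer that the rule does the opposite of its rationale; the text supports only that it falls short for courses of 3 or more days, and no course lengths are given.

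A second reply is that the loss of power depends on the endpoint. This also stands. The larger losses need a single qualifying period to classify a participant for the whole year. The Précis and Section 3 can be read that way, but Section 9.6 describes a monthly comparison of the last 30 days, and Hypothesis 3 in Section 1.1 refers to the 12-month follow-up.

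Third, the 45% is traced to Section 2.1, which cites recidivism of over 40% and mentions no exclusion of acute use. If the planning rates already include acute courses, the planned power is unchanged. The outcome would still mix the two kinds of use.

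Fourth, concomitant medications and adverse events are already collected, and Aim 2 is secondary in a trial powered for Aim 1. Both are true and both limit the weight of the point. Neither supplies a rule for classifying an episode.

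**Conclusion.** The mismatch between purpose and rule holds on the text. Followed as written, the plan counts acute courses of 3 or more days that Section 3 says should not count, and nothing described in Section 9.5.2 corrects this.

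The size is uncertain. It rests on an assumed acute-course rate and on planning rates assumed free of acute courses. With equal rates of 5% to 15%, power falls from 0.78 to between 0.72 and 0.60 under the whole-year endpoint. Under the monthly comparison the loss at 10% to 15% is about 1 to 3 percentage points.

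A reader might infer that Aim 2 is seriously underpowered for this reason, or that acute courses are common in this population. The documents support neither: they give no frequency, and they do not settle the endpoint. Nor is dilution the only possible direction, since unequal rates can widen the contrast. The firmer conclusion concerns interpretation: as described, the Aim 2 result cannot separate relapse from acute treatment. This should be corrected, and doing so is cheap.

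**What to change.** 1. Add one item to the TLFB: for each opioid episode, whether it was for a new injury or surgery.
2. Check the answer, blind to arm, against CPRS and the adverse-event and concomitant-medication records already collected. Use PAT only to confirm dispensing, since Section 9.5.2 describes it as a record of medications dispensed and does not say that it shows indication.
3. Pre-specify in Section 9.6 an analysis that does not count days documented for a new injury or surgery, reported beside the all-cause 3-day count.
4. Correct the Section 3 rationale to say that the main rule excludes only use on fewer than 3 days in 30.

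The cost is one interview item, the record check and one further analysis. Indication remains partly self-reported. The change does not restore power in the main analysis, which keeps the all-cause count; it lets Aim 2 also report the outcome that Section 3 describes, under a classification fixed in advance.
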